SUBJECT DEMOGRAPHICS**0 unresolved comment(s)**Age level of human subjects: (i.e., 6 mths.; 2yrs., etc.) to **Study Population:**

Describe the characteristics of the subject population, including age range, gender, ethnic background and health status. Identify the criteria for inclusion and exclusion.

Provide the following information:

- A description of the subject selection criteria and rationale for selection in terms of the scientific objectives and proposed study design;
- A compelling rationale for proposed exclusion of any sex/gender or racial/ethnic group;
- Justification for the inclusion of vulnerable groups such as children, prisoners, adults with impaired consent capacity, or others who may be vulnerable to coercion or undue influence.

Please consider these resources:

[NIH Diversity Policy](#)

[FDA Diversity Guidance](#) 

Specific Aim 1:

Based on our preliminary research, we anticipate enrolling 66% of all dyads, for a total of 1120 dyads. Once a clinic crosses from standard of care to PN in the stepped-wedge design, recruitment of all eligible parent-infant dyads in that clinic will begin. Prior to postnatal hospital discharge, parents whose infants fail their newborn hearing screening test are referred to university-based, private, or OCSHCN hearing centers for follow-up testing. The referral and contact information for these parents is collected and maintained by the state EHDI program. Within one week of postnatal hospital discharge, research personnel will contact by phone each parent referred to a OCSHCN clinic in the PN condition to describe the study, screen the parent-infant dyad for eligibility, and invite eligible dyads to enroll in the study. Informed consent will be obtained including permission to access infant hearing data from EHDI.

Inclusion criteria for parent-infant dyads:

1. Infant failed a hearing screening in one or both ears before postnatal hospital discharge
2. Infant was referred for follow-up diagnostic testing at one of the 10 participating CCSHCN clinics.
3. Parent able to speak English or another language using Cyracom, telephone interpreting service.

Exclusion criteria:

1. Children and parents live outside Kentucky or who will be moving out of Kentucky within the first three months of life.

Inclusion Criteria for Patient Navigators:

1. Age 21 years or older
2. Able to speak and read English
3. Willing to complete PN training and deliver PN.

Inclusion Criteria for Patient Navigators:

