Aim 1 is involving the recruitment of 1120 parent-infant dyads over the course of 4 years referred for hearing testing to Office for Children with Special Health Care Needs (OCSHCN) clinics all across the state of Kentucky. The research will occur within 10 OCSHCN clinic offices across the state. This is a expansion of research conducted within this location approved under IRB protocol. These patients are referred to those clinics from birthing hospitals at the time of birth because the child fails a newborn hearing test in the newborn nursery. This is one while the child is in the hospital but usually no more than 3-4 weeks after the child is born. Once the dyad is referred to that OCSHCN clinic, the clinic schedules them for their office visit in that clinic. The OCSHCN staff (not any of our research personnel) ask the parent about being contacted by the research personnel and may insert a small flyer on the study that would accompany the appointment reminder if parent would like further information. If they agree to being contacted then the clinic staff send the name and contact number of the dyad to our research staff to contact about participation in the study. We do not cold call anyone and we do not go through any records to identify subjects. The potential participants are given to us by our partners at the OCSHCN. We then contact them by phone and go through the verbal consent over the phone. We do ask parents for additional contact methods, such as email or other contact, such as text messaging and make contact up to 5 times to participate if parent does not answer or requests return call initially. After one phone conversation, we may try to text the parent with general information to gauge further interest in participation. The text message would recall the research personnel he or she spoke to, a brief summary of the study and to contact research personnel if interested. The text would be sent only after initial contact to verify the parent phone number is correct. We will attach this form to OCSHCN referral form. We will not be going through any medical records at that OCSHCN clinic where there are going to be seen before, during, or after participation in the study. The participants provides any important medical information on the study questionnaire once informed consent is obtained. We do not have any physical contact with the proposed participants as they are likely many miles away and we do not have research personnel at the clinic. Doing the consent over the phone is the

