a) Patient-level recruitment will involve all parents of infants who fail an infant hearing screening and are referred to an Office for Children with Special Health Care Needs (OCSHCN) clinic for outpatient audiological testing during the window in which that clinic is implementing the patient navigation (PN) intervention. Under a sequential rollout in steps of 6-month intervals, 10 OCSHCN clinics throughout Kentucky will be randomly allocated to cross from the control condition (standard of care) to the PN condition over the project period. (OCSHCN operates 11 total clinics geographically dispersed across the state; one clinic receives too few infant audiology referrals to be included in this study.) Randomization will be stratified by clinic patient population size. No randomization will occur at the individual level. By the study's end, all clinics will have participated in the PN intervention for a minimum of 1 year and a maximum of 4 years. We anticipate approximately 1700 failed newborn screening referrals to the 10 clinics during their time in the PN intervention condition (i.e., 50 six-month periods across all 10 clinics). Based on our preliminary research, we anticipate enrolling 66% of all dyads, for a total of 1120 dyads. This enrollment would reflect an average enrollment of 22.4 participants per clinic per six-month period of the intervention condition. Because collected data will pertain to both the infant and the parent, both will be considered research participants; thus, the total planned sample size is 2240. Study eligibility will be assessed via telephone by a member of the research team who is CITI-trained in human subjects protection, and parents will provide verbal consent for their participation and their child's participation in the study. Approximately 40 already-enrolled parents will also participate in key informant qualitative interviews after a separate informed consent process. No additional inclusion/exclusion criteria will apply. At no time during this study will prospective dyads be selected by examining medical records. Dyads will be referred by the various OCSHCN clinics, and not contacted by study personnel until that time. Additionally, no survey results, or interview information (if applicable), will be added to patient records and will only be held by research personnel for the time period required by the IRB before they are destroyed.

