Parent-Infant Dyads: As part of the same phone call to obtain parental informed consent, a trained research assistant will administer baseline measures of knowledge of hearing loss, self-efficacy for obtaining follow-up testing, and perceived barriers to follow-up testing. Alternatively, the parent can choose to complete the baseline measures via REDCap links. Following completion of baseline measures, parents will be contacted by the PN to initiate intervention delivery. Post-test measures will be administered by phone by a research assistant or via REDCap 16 weeks after birth – one month after the 3-month target deadline for diagnostic testing has passed. The research assistant administering post-test measures will not have access to data regarding parents' follow-up with diagnostic testing. Parent participants will be compensated \$20 for each set of completed measures (i.e., at baseline and at post-test assessment). These data will be shared with the CAB quarterly and recommendations on additional PN training or PN modifications will be observed. At no time during this study will prospective dyads be selected by examining medical records. Dyads will be referred by the various OCSHCN clinics, and not contacted by study personnel until that time. Additionally, no survey results, or interview information (if applicable), will be added to patient records and will only be held by research personnel for the time period required by the IRB before they are destroyed.

Parent-Infant Measures: Secondary effectiveness outcomes include parent participants' knowledge, self-efficacy, and barriers regarding obtaining follow-up diagnostic testing for their infant. We will also obtain EHDI data for all enrolled infants until their one-year birthday (or until data collection ends) to determine the time from birth to initial completed diagnostic assessment, number of no-show appointments, and number of rescheduled appointments. We will also collect data from EHDI to allow for control comparison of those infants who do not participate in the program to compare outcomes regarding follow-up diagnostic testing. From this control data, we will be conducting analyses looking at the impact of the COVID-19 pandemic on diagnostic testing and newborn hearing screening throughout the state of Kentucky. We will be comparing pre-COVID data with peri-COVID data. Additionally, we will look for racial & ethnic differences in the rates of follow up testing and screenings.

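### The EHDI contrast of enrolled infants with non-participants can show a difference without any navigation effect; compare the remaining EHDI outcomes by randomised clinic-period instead

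*Combined protocol and SAP*

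**What the plan says.** The combined protocol and SAP (Research Procedures, Parent-Infant Measures) first plans EHDI follow-up for enrolled infants up to the first birthday or the end of data collection. The outcomes are time from birth to the first completed diagnostic assessment, no-shows and reschedules. It then adds: "We will also collect data from EHDI to allow for control comparison of those infants who do not participate in the program", with the purpose "to compare outcomes regarding follow-up diagnostic testing". The same data are to serve a pandemic analysis ("We will be comparing pre-COVID data with peri-COVID data") and a look at racial and ethnic differences.

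On who becomes a participant:

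- Study Population, Specific Aim 1: once a clinic crosses to PN, "recruitment of all eligible parent-infant dyads in that clinic will begin".
- Study Population, later paragraph on recruitment: "If they agree to being contacted then the clinic staff send the name and contact number of the dyad to our research staff". Staff then "make contact up to 5 times to participate if parent does not answer", and the parent gives verbal consent.
- Informed Consent Process, item a): "No randomization will occur at the individual level", and "we anticipate enrolling 66% of all dyads, for a total of 1120 dyads" out of roughly 1700 referrals in PN periods.

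The trial's own control condition is set elsewhere. Study Design, Specific Aim 1, defines it by clinic and time: standard of care until the clinic starts PN. Research Procedures, Specific Aim 1, Clinics, takes the monthly clinic-level proportion of non-adherent referrals as the primary outcome and compares PN-condition with control-condition data. Aim 3 takes its effectiveness measure from those same clinic-level rates.

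**The concern.** The stepped wedge randomises the time at which clinics cross. It does not randomise which families enrol. A contrast defined by participation therefore has no protection from the design. Parents who can be reached and who consent may also be the parents who keep appointments, or they may not; the documents do not say.

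The control side is open as well. The wording fits at least three groups: PN-period infants who were not enrolled, infants referred before their clinic crossed, and infants referred to university or private centres. The enrolled side is self-selected whichever is meant. With pre-crossing referrals, calendar time is added, because within a clinic they always come before the enrolled infants, and the plan itself expects a pandemic effect over the study.

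At stake is interpretation. If the contrast is labelled a control comparison and shows a difference, a reader cannot separate PN from self-selection.

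**Working it through.** **1. The plan's enrolment figures** (Informed Consent Process, item a)

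- 0.66 × 1700 = 1122, against 1120 stated; 1120/1700 = 65.9%.
- 1120 / 50 clinic-periods = 22.4, as stated; 2 × 1120 = 2240, as stated.
- Not enrolled: 1700 − 1120 = 580, or 34.1% of PN-period referrals. Some of these may be ineligible rather than unreached or unwilling.

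**2. Spurious difference with no PN effect**

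Assume no time trend. Let the adverse outcome average x in enrolees and x + d in non-enrolees. The documents do not give d.

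- Controls are PN-period non-enrolees: (x + d) − x = d.
- Controls are all pre-crossing referrals: 0.66x + 0.34(x + d) − x = 0.34d. In general the factor is 1 minus the enrolment proportion.
- Controls are infants referred elsewhere: no figure is possible, because type of centre differs too.

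| Assumed d (percentage points) | −10 | 0 | 5 | 10 | 20 |
|---|---|---|---|---|---|
| Against PN-period non-enrolees | −10 | 0 | 5 | 10 | 20 |
| Against all pre-crossing referrals, 66% enrolled | −3.4 | 0 | 1.7 | 3.4 | 6.8 |
| Same, 50% enrolled | −5.0 | 0 | 2.5 | 5.0 | 10.0 |
| Same, 80% enrolled | −2.0 | 0 | 1.0 | 2.0 | 4.0 |

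The result does not depend on x. It holds for a proportion or a mean count, but does not carry over to a median or hazard for time to diagnosis, which may be censored.

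**3. Would a modest gap be declared significant?**

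Take a binary follow-up outcome, 1120 enrolees against 580 non-enrolees, and no PN effect. Assumptions: two-sided 5% test, infants independent (clinic clustering ignored), overall non-adherence 38% (the earlier trial's standard-of-care figure in Background), and an odds ratio OR for non-enrolees. Solve (1120/1700)·pE + (580/1700)·pN = 0.38. The chance of significance is Φ[(gap − 1.96·SE0)/SE1], where SE0 is the pooled and SE1 the unpooled standard error.

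- OR 1.1: 37.2% v 39.5%, gap 2.3 points, significant in about 15% of trials.
- OR 1.25: 36.2% v 41.5%, gap 5.3 points. SE0 = 0.0248 and SE1 = 0.0250, so (0.0529 − 0.0487)/0.0250 = 0.17, or about 57%.
- OR 1.5: 34.7% v 44.4%, gap 9.7 points, about 97%.

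A gap of about 4.9 points gives a 50% chance, and about 7.0 points gives 80%. With 59.4% overall (100 − 40.6, the national figure in Background), the gaps for these odds ratios are 2.3, 5.3 and 9.6 points, with the same percentages.

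**4. The clinic-period contrast**

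If both sides hold all referrals, each averages 0.66x + 0.34(x + d) when PN has no effect and time does not matter. The expected difference is 0 for any d. The price is dilution. As an example, the earlier trial's gap of 38 − 7 = 31 points would appear as 0.66 × 31 = 20.5 points if it held in enrolees and PN did nothing for the rest.

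**The case against.** The strongest reply is that the plan contains no such analysis to criticise. The sentence describes data collection; it gives no model, estimand or test, and does not state outright that enrolled infants form the other side. The effectiveness outcomes labelled secondary are parents' knowledge, self-efficacy and barriers. The uses then listed for the control data, pandemic effects and racial or ethnic differences, need no enrolled versus non-enrolled contrast. For non-adherence, the clinic-condition comparison is already the primary design. The application also defers to a grant submission that was not supplied and may define the comparator.

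Most of this stands, and it limits the point. The pairing is an inference from adjacent sentences, though the natural one, because the stated purpose is a control comparison of follow-up testing. The remedy is new only for time to diagnosis, no-shows and reschedules. The size is an illustration resting on an assumed d.

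The recruitment text is also inconsistent. One paragraph of Study Population has research staff phoning each referred parent, while a later one requires agreement to contact first. One selection step is therefore uncertain, but consent is voluntary under either account, so selection remains possible.

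A reader might go further and infer that the trial's effectiveness result is confounded by self-selection, or that the bias favours PN. The documents support neither. The primary outcome counts referrals by clinic and month under the randomised crossing, Aim 3 uses the same rates, and nothing shows which way enrolees differ.

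**Conclusion.** The point holds for the ancillary EHDI comparison only. As the supplied text stands, it most naturally contrasts a self-selected group with non-participants whose clinics and periods are not named, and it can show a difference when PN does nothing. The spurious difference is d against PN-period non-enrolees and about 0.34d against all pre-crossing referrals, given 66% enrolment and no time trend. It is zero if enrolment is unrelated to follow-up, and its size and sign cannot be obtained from the documents. The primary analysis and Aim 3 effectiveness are unaffected, and no use of this comparison as evidence for PN is stated. The matter is worth correcting because the design already supplies a less biased contrast for the same outcomes.

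**What to change.** For time from birth to first completed diagnostic assessment, no-shows and reschedules, compare all infants referred in PN clinic-periods, enrolled or not, with all infants referred in standard-of-care clinic-periods of the same 10 clinics. Adjust for clinic and calendar period, and treat time to diagnosis as possibly censored. If a participant versus non-participant contrast is kept, name the clinics and periods that supply the controls, say whether those families were invited, and report it as observational only.

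Enrolment is recorded as ended, so this changes analysis and not conduct. The costs are:

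- **A different question.** The estimate becomes the effect of offering PN, diluted by the roughly 34% not enrolled.
- **Data access.** Clinic and referral date are needed on the EHDI records. Study Population ties access to an infant's EHDI data to parental consent, so infant-level data for non-consenting families need an access check first.
- **Fallback.** If access is refused, use clinic-period aggregates for no-shows and reschedules; time to diagnosis would then need binned data or be left out.

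### The pre- versus peri-COVID comparison draws on non-participants, whose make-up at the 10 trial clinics shifts as navigation rolls out, so rollout can pass for a pandemic effect on diagnostic testing

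*Combined protocol and SAP*

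**What the plan says.** The analysis is described in the last sentences of Parent-Infant Measures (Research Procedures, Specific Aim 1). The source is set first: "We will also collect data from EHDI to allow for control comparison of those infants who do not participate in the program". The pandemic analysis is then drawn from that source: "From this control data, we will be conducting analyses looking at the impact of the COVID-19 pandemic on diagnostic testing and newborn hearing screening". Its scope is given as "diagnostic testing and newborn hearing screening throughout the state of Kentucky". The contrast is one sentence: "We will be comparing pre-COVID data with peri-COVID data". No cut date, peri-COVID window, model, clinic term or rule for clinics that have crossed is given.

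Two other places decide who counts as a non-participant:

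- Study Population, Specific Aim 1: "Once a clinic crosses from standard of care to PN in the stepped-wedge design, recruitment of all eligible parent-infant dyads in that clinic will begin". Nobody can enrol at a clinic before it crosses.
- Informed Consent Process, item (a): "we anticipate enrolling 66% of all dyads, for a total of 1120 dyads". The same item expects about 1,700 referrals over 50 six-month clinic-periods of navigation, and says every clinic spends between 1 and 4 years in navigation.

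**The concern.** Membership of the control pool depends on trial participation, and participation depends on calendar time. Before a clinic crosses, all its referrals are non-participants. Afterwards the expected 66% who enrol leave the pool, and the clinic contributes only families who declined, did not agree to be contacted or were not reached. Crossing is one-way, so this drift runs in the same direction as the pre- to peri-COVID contrast.

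The remaining third need not resemble all referrals, because the plan passes on contact details only when parents agree and makes up to five contact attempts. If their follow-up differs in either direction, the comparison shows a change between the two eras with no pandemic effect at all. Nothing in the stated analysis separates the two.

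**Working it through.** **Inputs from the documents.** About 1,700 referrals in the navigation condition, 1,120 dyads enrolled and 50 clinic-periods (Informed Consent Process, item (a)); 10 clinics crossing in 6-month steps, with 1 to 4 years in navigation (same item); 38% standard-of-care non-adherence in the investigators' previous randomised trial (Background).

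**The plan's own figures.** 1,700 × 0.66 = 1,122, which agrees with the stated 1,120. 1,120 / 50 = 22.4 per clinic-period, as stated. 1,700 / 50 = 34 referrals per clinic-period. The enrolled fraction is e = 1,120 / 1,700 = 0.659, leaving 1 − e = 0.341.

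**Assumptions, not in the documents.** Equal referrals per clinic; seven steps (8 down to 2 half-years of navigation) with at least one clinic at each; one all-control half-year first; pandemic onset after half-year 1, 2 or 3; non-adherence of 38% in uncrossed clinics and 48% in the not-enrolled. The 48% implies (38 − 0.341 × 48) / 0.659 = 32.8% in those who would enrol, had they received standard care.

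**Step 1: make-up of a 10-clinic pool.** With c clinics crossed, the not-enrolled share is c(1 − e) / [(10 − c) + c(1 − e)]:

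- c = 0: 0%
- c = 5: 25%
- c = 7: 44%
- c = 8: 58%
- c = 9: 75%
- c = 10: 100%, which holds for at least the last year

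**Step 2: one rollout that fits the text.** Clinics crossing 1, 2, 1, 2, 1, 2, 1 give 8 + 14 + 6 + 10 + 4 + 6 + 2 = 50 clinic-periods. With onset after two half-years:

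- Before onset: 646 infants from uncrossed clinics and 11.6 not enrolled, a share of 11.6 / 657.6 = 1.8%.
- 12 months after onset: 442 and 81.2, a share of 15.5%.
- All periods after onset: 714 and 568.4, a share of 44.3%.

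The spurious change is (share after − share before) × (48 − 38). That is 1.4 points for the 12-month window and 4.3 points if every later period counts.

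**Step 3: all eight allocations that meet the assumptions, three onsets each.** The share before onset is 0–6%.

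| Peri-COVID window | Share after onset | Spurious change at 48% |
|---|---|---|
| 12 months | 6–29% | 0.6–2.6 points |
| 24 months | 14–41% | 1.4–3.8 points |
| To end of trial | 36–55% | 3.6–5.2 points |

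Dropping the all-control half-year changes the last row to 3.5–6.4 points.

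**Step 4: direction.** The change scales with the difference from 38%. At 38% in the not-enrolled it is zero. At 30% the factor is −8 instead of +10, so 0.6–5.2 becomes about −0.5 to −4.1 points, an apparent improvement.

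**Step 5: statewide pool.** Let f be the fraction of Kentucky failed-screen referrals that go to the 10 clinics (not in the documents). After full rollout the share is f(1 − e) / [(1 − f) + f(1 − e)]:

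- f = 0.25: 0.085 / 0.835 = 10%, a change of 1.0 point at 48%
- f = 0.50: 0.171 / 0.671 = 25%, a change of 2.5 points
- f = 0.75: 0.256 / 0.506 = 51%, a change of 5.1 points

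**The case against.** The strongest reply is that the analysis is described as statewide, and Study Population says failed-screen infants also go to university-based and private centres. On that reading the 10 clinics supply only part of the pool and the shift is diluted, as step 5 shows. This stands as a limit on size. It does not remove the problem, because trial-clinic infants would still be selected by participation.

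Several stronger conclusions are tempting, and the documents do not support them:

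- *That the pool turns into mainly decliners.* A majority is reached only in a 10-clinic pool, and only once about 8 of 10 clinics have crossed. The not-enrolled also include families who were never reached or did not agree to contact.
- *That the bias must look like a worsening.* No adherence figure for the not-enrolled is given. Families who feel no need of help might follow up better.
- *That the screening question cannot be answered.* This would follow only if the pool were limited to infants meeting the trial's inclusion criterion: "Infant failed a hearing screening in one or both ears before postnatal hospital discharge". The text does not say so, and its statewide wording points the other way. Screening also precedes referral and navigation, so rollout cannot distort it by this route.

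It is also fair to say that this is an added analysis. The primary outcome is the monthly clinic-level proportion of non-adherent referrals, which does not select on participation.

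**Conclusion.** The point holds for diagnostic testing. As written, the pool is selected on participation, its make-up at the trial clinics changes with calendar time, and no stated term or restriction separates rollout from the pandemic.

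The size is open. Under the assumptions above, with 48% against 38%, it is about 0.6–5.2 points for a 10-clinic pool and about 1–2.5 points after full rollout for a statewide pool with 25–50% of referrals at these clinics. It is zero if the not-enrolled do not differ, and opposite in sign if they follow up better. The window, the onset, the rollout calendar and the not-enrolled rate are all assumed, so these figures illustrate the problem and do not estimate it. For newborn screening, only a clarification of the data source is needed.

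**What to change.** Select the COVID dataset by birth month and referral site, not by participation, and state the cut date and the peri-COVID window.

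- **Diagnostic testing, main analysis:** use all EHDI failed-screen referrals, enrolled or not, including those to non-OCSHCN centres, with clinic and the clinic's navigation status at the time in the model.
- **Diagnostic testing, sensitivity analysis:** limit to clinic-months still in standard of care, plus the non-OCSHCN centres. This does not rely on modelling the navigation effect correctly.
- **Newborn screening:** state that the data are all Kentucky births in EHDI by birth month.

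The cost is a broader EHDI data request and a few sentences of analysis text. The restricted analysis loses most late OCSHCN data. Under the seven-step assumption about 62–78% of post-onset clinic-periods have crossed (for example 50 of 80 with onset after one half-year), and all have in at least the last year. That is why it should be the sensitivity analysis and not the main one.
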